5.3. Participant Recruitment Procedures

The study will employ the following procedures, which have been successfully utilized in Friends Research Institute's (FRI's) previous randomized trials implementing pharmacotherapy with prisoners. Maryland Department of Correction (DOC) personnel will schedule project orientation appointments with research staff for the Baltimore area prison inmates with less than 60-90 days to serve. Group orientation sessions will be conducted at each prison, in which research staff will explain study procedures and eligibility requirements. Potentially interested inmates will then meet individually with research staff for an in-depth discussion of the purposes, procedures, risks, and benefits, of study participation, and to make a preliminary determination of eligibility, subject to confirmation during the physical examination (see below). Immediately after providing informed consent, each potential participant is scheduled for administration of the baseline measures. Following baseline assessment, which is used, in part, to confirm eligibility regarding histories of opioid addiction and nature and severity of medical and psychiatric problems, each potential participant will meet with the project medical staff for a medical history, physical examination, and laboratory tests to confirm eligibility and suitability for XR-NTX administration, and to discuss the potential risks and benefits of study participation. Individuals who do not meet medical eligibility based on physical examination or do not wish to initiate XR-NTX following a discussion of this treatment with the study physician will not be enrolled into the study. Potential participants who are determined medically eligible and remain interested in participating in the study will then be randomly assigned to one of the two treatment conditions (see **Random Assignment**, below). Finally, because of the possibility of coercion when working with prisoners, the study RAs will emphasize that the decision to participate or not will not affect the prisoner's status, institutional privileges, or release date. In addition to group orientations we will post IRB approved study flyers in the five prisons (these will be pre-approved locations decided upon by prison administration at each prison).

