1.0 SPECIFIC AIMS

Heroin use has risen significantly over the past 11 years¹ with heroin overdoses increasing by 23%.² Opioid use disorders are a severe problem among jail and prison inmates throughout the world.³⁻⁷ In the United States, there are over 1.5 million state and federal prisoners,⁸ of whom an estimated 12-15% have histories of OUDs.⁹ Moreover, scarce resources are provided for corrections-based substance use treatment in many nations, and many inmates with OUDs remain untreated;^{7,10} and less than .1% receive agonist treatment.¹¹ Correctional health officials, treatment providers, and policy makers need innovative, effective, and cost-beneficial approaches to help inmates with OUD successfully transition to the community.

We recently completed a Phase 4 pilot, open-label study of long-acting injectable naltrexone (XR-NTX), funded by Alkermes, with prisoners with pre-incarceration OUD. In this study, involving one XR-NTX injection in prison followed by 6 monthly injections in the community, XR-NTX was feasible; all 27 participants got their first injection.¹² XR-NTX was acceptable to correctional officials; it did not disrupt security and other prison routines and there was no concern about its diversion. An expected benefit of XR-NTX was opioid blockade for 30 days; there were no overdoses in the first month post-release. However, an important challenge was that while 78% of participants received their first community injection, only 37% received their 5th and 6th injections. In our multi-site study of parolees/probationers funded by NIDA,¹³ 308 participants were randomized to XR-NTX across five sites in which 95% received the first injection; 65% received their 5th and 59% received their 6th injections. XR-NTX adherence rates were higher in parolees and probationers and roughly equal to opioid agonist treatment but still dropped off by month 6. Also, most parole/probation participants were recruited from community treatment programs and were nearing completion of treatment at study entry, which meant that they were more likely to have more stable lives than newly released prisoners. These results and many stressors faced by newly released prisoners, noted below, suggest that enhancements to prison initiation of XR-NTX are needed in order to ensure continued adherence to XR-NTX treatment.

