2.7.3. A Phase 4, Pilot, Open-label Study of VIVITROL® in the Prevention of Re-arrest and Re-incarceration. This was a Phase 4B, open-label, longitudinal, single cohort, pre-post study. Pre-release opioid-dependent inmates from four Maryland area prisons (three for men and one for women) receive one injection of XR-NTX prior to release from prison and are then offered six monthly injections of XR-NTX for six months post-release. Following prison release, participants were seen for study visits and receive XR-NTX at Glenwood Life Counseling Center in Baltimore, MD. Participants were assessed at 10 time points: at screening (study entry: approximately one month prior to release from prison), at baseline (approximately 1 week prior to release), and then monthly for 6 treatment visits, an end-of-treatment visit, and a safety follow-up visit following their release from prison. We provided XR-NTX to 27 prisoners, of whom 100% received their first injection in prison; 21/27 (77.8%) received their first community injection, 18/27 (67%) received their second community injection; 13/27 (48%) received their third community injection; 11/27 (41%) received their 4th community injection, 10/27 (37%) received their 5th community injection, and 10/27 (37%) received their 6th community injection. Over the one-year enrollment period in this study, 97 individuals were screened for interest; 23 were initially not eligible, and 74 consented. Of these 74, 9 refused, 6 were released early and/or transferred to other prisons; 2 failed to meet the OUD criteria and 3 were positive for buprenorphine (all would have been ineligible for the presently proposed study). Fifteen inmates were excluded for medical reasons, 7 for psychiatric reasons and 5 for both psychiatric and medical reasons. According to the study physician and Co-I on the proposed study, [name], most, if not all, of these 27 excluded for medical and/or psychiatric reasons would have been eligible for the presently proposed study, as the proposed study would not exclude individuals with appropriately treated medical and/or psychiatric conditions. Results indicate participants completing 6 compared to participants completing less than 6 injections were less likely to test positive for opioids in the community (0% vs. 63%, respectively; $p=.003$). Although not statistically significant, individuals who did not complete all 6 injections were more likely to be re-arrested compared to those completing all 6 community injections (31% vs. 0%, respectively; $p=.12$).¹² The limitations of this study included a small sample size which was highly selective and lack of a comparator group. Finally, because the rather long list of exclusion criteria were mandated by the funding agency, the ability to generalize results is limited. The proposed study will have a larger sample size, comparator group, and less stringent exclusion criteria.

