5.2. Participant Eligibility: Inclusion/Exclusion Criteria

Eligible inmates must meet the following criteria: (1) adult male or female inmate at BCF, DRCF, BCCC, MCIW, CMCF, MCTC, or RCI and be eligible for release within 30 days; (2) history of opiate disorder [meeting DSM-V criteria of dependence at the time of incarceration; individuals who do not meet criteria at time of incarceration and become addicted during incarceration will be eligible]; Inmates not meeting the opioid-dependence criterion will be eligible if they were treated in an opioid agonist treatment program during the year before incarceration. (3) suitability for XR-NTX treatment as determined by medical evaluation; (4) currently opioid-free by history, with negative urine for all opioids and no signs of opiate withdrawal; (5) willingness to enroll in XR-NTX treatment in prison [not currently in or planning to pursue agonist (methadone, buprenorphine) treatment at release]; and (6) planning to live in Baltimore City or County (individuals outside of Baltimore City/county will be allowed to participate as long as they agree to travel to the treatment clinic if randomized to OTX). Inmates with one or more of the following conditions will be excluded from the study: (1) Liver function test levels greater than three times normal (note: if a blood specimen is unable to be drawn the individual will not be excluded from participation); (2) Active medical illness that may make participation hazardous (e.g., unstable diabetes, heart disease). Adequately treated medical conditions are acceptable; (3) Untreated psychiatric disorder that may make participation hazardous (e.g., untreated psychosis, bipolar disorder with mania). Adequately treated psychiatric disorders and appropriate psychotropic medications will be allowed; (4) History of allergic reaction to XR-NTX; (5) Current chronic pain diagnosis for which opioids are

prescribed; (6) creatinine above normal limits; (7) pregnancy (for women); (8) Breast-feeding (for women) (9) suicidal ideation (within the past 6-months); and (10) Body Mass Index (BMI) > 40.

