5.6. Medical Services in Prison

5.6.1. Treatment Clinic. Glenwood Life Counseling Center (GLCC) has been in continuous operation for 41 years. It is a State of Maryland- and CARF-certified outpatient drug treatment program that treats over 600 patients. GLC provides individual and group drug abuse counseling, HIV assessment and risk-reduction counseling, and a limited amount of family-based therapy. Its medical director, [name], served as the study physician on the PI's prison methadone, buprenorphine, and XR-NTX studies. The clinic is well-suited to continue its collaboration on the proposed study, in which it will provide XR-NTX services in the prison as well as in the community. [name] will perform all prison medical examinations and the nursing staff will provide prison-based injections under his supervision within 10 days of release.

5.6.2. Pre-release extended-release XR-NTX. XR-NTX treatment will likewise be administered by the nursing staff of GLCC under [name] supervision. Participants will receive one injection within 10 days prior to release. Long-acting, injectable naltrexone (Vivitrol®) will be used, at a dose of 4cc (380mg of

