naltrexone), administered by intramuscular injection to the buttocks (alternating sides monthly). Note: Participants can request to receive the intramuscular injection to the buttocks on the same side at each monthly visit. Vivivivrol® has the advantage of being FDA-approved for treatment of alcohol and opioid dependence, hence commercially available with strong safety data. Participants who deny opioid use in the past 10 days and who provide a specimen that tests negative for opioids on an instant urine test will receive a naloxone challenge test (Note: participants will receive two urine drug screens after consent: 1) one within 7-10 days of the injection; and 2) on the day of the injection). Naloxone is a short-acting opioid antagonist. This test consists of an intravenous (or intramuscular for participants' without venous access) injection of a 1.0mg of short-acting naloxone followed by a 20-minute observation period. A positive test will cause the temporary (up to 40 minutes) appearance of opioid withdrawal symptoms. Following a negative naloxone test, participants will be administered a low dose of oral naltrexone (12.5 mg) to further determine whether they will be able to tolerate depot naltrexone. If the participant has withdrawal symptoms in response to either the naloxone test or the oral naltrexone dose, the study physician will treat these symptoms with other medications. The medical staff of all prisons are highly experienced in treating opioid withdrawal, will be fully aware of the ongoing study, and will be able to provide symptomatic treatment to participants in the unlikely event that it is needed when study staff are not on the premises. Such issues may consist of the following: 1) withdrawal; and/or 2) injection site reaction. Prior to discharge, participants will receive an information card about naltrexone to carry with them at all times which will alert any medical providers about the characteristics of naltrexone. Ten days before anticipated release from prison, each participant will have an exit interview with the study's Research Assistant (RA). The RA will provide each such participant with a card with the address of GLCC outlining their schedule for their six monthly injections in the community. In addition, those randomized to XR-NTX+MMTx will receive a pamphlet 10 days before from the study RA detailing the procedures and operations of receiving medication at their place of residence. Follow-up injections will be scheduled 28 days (4 weeks) after first prison injection.

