6.0. Statistical Analyses

6.1. Guiding Principle. Although the description of the statistical approach that follows is more in line with the language associated with a ‘traditional’ superiority trial, we endorse the “sensible formulation of the significance test” proposed by Jones and Tukey.⁹⁷ These authors outline an approach to significance testing that focuses not on the rejection of a null hypothesis, but on determining whether the data favor a determination of superiority or inferiority. As part of their approach, they suggest reporting not only a test statistic and its associated probability value but also a confidence interval and an effect size related to the determination of any difference. It would be our intention in reporting our results to adhere to Jones and Tukey’s suggestions.

6.2. Intent-to-Treat Approach. All analyses will be conducted on available study-related data from all participants, regardless of whether or when they drop out of treatment; i.e., the intent-to-treat population is all persons consented and randomized to the study.

6.3. Outcome Measures. Except for criminal justice records, collected at study conclusion, outcome data will have been collected monthly during the project: at baseline (study entry), and at 1, 2, 3, 4, 5, 6, 7, and 12 months following release from prison (see **Figure 2**, above). The resulting dependent variables will be of three distinct types: 1) continuous random variables (e.g., RAB scale scores), assumed to follow a normal distribution; 2) discrete random variables (e.g., number of days of criminal activity), assumed to follow a Poisson distribution; and, 3) dichotomous variables (e.g., treatment adherence, urine drug screening results), assumed to follow a binomial distribution. [All distributional assumptions will be evaluated prior to the conduct of all analyses, and if such assumptions are not met, assumptions will be modified and statistical methods chosen accordingly, and/or outcome measures transformed appropriately. For example, it may be necessary to allow for under- or over-dispersion in the logistic and Poisson regression analyses, or use zero-inflated Poisson or negative binomial models rather than a Poisson model for the count variables.]

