6.7. Power. Stroup¹⁰¹ (also see Littell et al.¹⁰²) has outlined a four-step procedure to estimate power for general linear mixed models, which can also be applied to generalized linear mixed models as occur in the proposed study. This procedure was implemented in the current case. For each of the number of Times outcomes were measured (4, 5, 6, 7, or 9), three datasets for each hypothesis were created, assuming the dependent variable was continuous and normally distributed, discrete and Poisson distributed, or dichotomous and binomially distributed. For the normally distributed case, the only non-null effect in the model was the hypothesized effect of interest, with the XR-NTX-OTx condition mean set at 1 at Time 1, decreasing by .1 at each subsequent Time point, while the XR-NTX+MMTx condition means were set at 1 at Time 1, and then adjusted to reflect “small”¹⁰³ mean differences (.2 of the standard deviation at subsequent Time points) consistent with the hypothesis of interest. [Time was not included in the estimation of power for the criminal justice outcomes because these outcomes are measured only at 12-month post-baseline assessment.] Similar specifications were made for the datasets with outcomes following the Poisson and binomial distributions. Finally, observations were dropped from the data consistent with the expected loss of approximately 10% of participants at the 12-month assessment (see **Participant Attrition**, above). Hence, power was estimated for a design in which the effects were unbalanced in a manner similar to what was expected to occur in the proposed research. Therefore, simulations were conducted under what might be considered “worst-case scenarios.” Power was then estimated for three different covariance structures (compound symmetric heterogeneous, first-order autoregressive heterogeneous, and unstructured) of the observations over Time. [Covariance structures can be specified for GLiMM models independent of the location (e.g., mean) structure, so it was only necessary to create a single dataset for the three cases.] Assuming a sample size of 240 and $\alpha=.05$, the resulting power values ($1 - \beta$) for the Treatment Condition X Time effect varying between .81 and .85 in the simulations. From a more rudimentary and slightly less accurate perspective, assuming the primary outcome measures follow a normal distribution rather than binomial or Poisson distributions, power calculations based on the set correlation method¹⁰⁴ can be used to calculate effect sizes for desired power, including under the extremely conservative assumption that no other effect in the model is significant (with the resulting effect size estimates likely to be slight underestimates). In this case, assuming $\alpha=.05$ and $N=216$ due to attrition (see **Participant Attrition**, above) in order to remain conservative, an effect size of $f^2=.037$ in the population associated with a Treatment Condition main effect for statistical models in which there is no Time effect (e.g., reincarceration) and effect sizes ranging from a minimum $f^2=.046$ to a maximum $f^2=.072$ for the Treatment Condition X Time effects associated with the 4, 5, 6, 7, or 9 Time points for statistical models in which there is a Time effect, would yield a power of .8 for the respective effect. These effect sizes fall toward the “small-to-medium” range, with $f^2=.02$ considered a “small” effect and $f^2 = .15$ a “medium” effect.¹⁰³ In other words, and imprecisely, under the assumption that the effect in the population was $\geq .037$ or $\geq .072$, for the Treatment Condition and Treatment Condition X Time effects, respectively, there is an 80% chance of concluding that effect is significant if α is set to .05 and 216 participants are assessed at 12-month follow-up. *Power calculations do not utilize any estimates of treatment efficacy from prior studies. This latter approach to power analysis, although once popular, is often quite limited, as is the case for the proposed study, in that prior studies may have examined populations that are not comparable to the population in the proposed study and/or do not include the same experimental or control conditions, and in all cases, the effect sizes reported in prior studies are generally subject to wide fluctuation due to sampling variability.*¹⁰⁵ Power was calculated to detect a stated effect size, as detailed in the proposal, an approach consonant with more recent writings regarding power analysis.

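### On the natural reading, randomisation comes before medication consent and the injection-day checks, so people who never start XR-NTX stay in both arms and cost power

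*Combined protocol and SAP*

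**What the plan says.** **Entry.** Section 5.2 requires the inmate to be "currently opioid-free by history, with negative urine for all opioids and no signs of opiate withdrawal" and eligible for release within 30 days.

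**Randomisation.** Section 5.3 places history, physical examination and laboratory tests first; those who are cleared and still interested "will then be randomly assigned to one of the two treatment conditions". Section 4.1 gives the same order. In 5.4 the study physician opens the envelope, announces the arm, and then obtains consent to start medication.

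**Checks before the injection.** Section 5.6.2 says "participants will receive two urine drug screens after consent": one 7-10 days from the injection and one on the day. A negative urine leads to the naloxone challenge, and a negative challenge leads to the oral naltrexone test. On the injection itself: "Participants will receive one injection within 10 days prior to release". The same section gives the mobile-arm pamphlet 10 days before release, so the arm is known by then.

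**Analysis and power.** Section 6.2 states that "the intent-to-treat population is all persons consented and randomized to the study". The power statement in 6.7 holds "if α is set to .05 and 216 participants are assessed at 12-month follow-up", which is 240 less 10%.

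**The concern.** Treatment before release is the same in both arms apart from the pamphlet. The arms differ in where the community injections are given. Someone who never receives the prison injection has no scheduled route to community injections: 5.6.2 dates them from the first prison injection, and no section provides for a first injection after release. Such a person cannot show a mobile-versus-clinic difference, yet is counted in the arm assigned.

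This is not the loss allowed for in 6.7. That allowance removes observations missing at 12 months. A non-starter can be fully followed up and enters the adherence analysis with no injections. The effect is to shrink the contrast on adherence and on the outcomes expected to follow from it. No section says how a randomised person who fails a challenge, declines medication or leaves the prison early is to be handled.

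**Working it through.** **1. Order of events**

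| Step | Where | Position relative to randomisation |
|---|---|---|
| History, examination, laboratory tests | 5.3 | before |
| Envelope opened | 5.4 | the randomisation itself |
| Consent to medication | 5.4 | immediately after |
| First urine screen | 5.6.2 | not stated |
| Injection-day urine, naloxone challenge, oral naltrexone test | 5.6.2 | after, on the natural reading |
| Prison injection | 5.6.2 | after, within 10 days of release |

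No section gives the interval from randomisation to injection. The pamphlet does bound it. The mobile arm is known 10 days before release and the injection falls within those 10 days, so randomising after the injection-day checks would fit only if everything happened on day 10, against the order in 5.3 and 5.4.

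**2. Reproducing the plan's power**

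Inputs from 6.7: α = .05, N = 240 × 0.9 = 216, f² = .037 for the Treatment Condition main effect. With a noncentral F on 1 and 214 df and λ = f² × N = .037 × 216 = 7.99, power is .804. The stated .80 reproduces.

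**3. Adding non-starters**

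Assumptions, neither in the documents: a share q of those randomised never starts, in both arms alike; and f² = .037 describes the effect among starters, with no arm difference among non-starters. The mean difference is multiplied by (1−q), so f² becomes .037 × (1−q)². The number to randomise to restore the stated power is 240/(1−q)².

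| q | f² | λ = 216 f² | Power | Randomise to restore |
|---|---|---|---|---|
| 0 | .0370 | 7.99 | .80 | 240 |
| 2% | .0355 | 7.68 | .79 | 250 |
| 5% | .0334 | 7.21 | .76 | 266 |
| 10% | .0300 | 6.47 | .72 | 297 |
| 14% (9/63) | .0272 | 5.87 | .67 | 327 |

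For Treatment Condition × Time with 9 time points (f² = .072, planned at .80), the same dilution gives about .78, .75, .69 and .64.

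**4. Where q might lie**

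The only proxy is the pilot in 2.7.3. Of 74 who consented, 9 refused, "6 were released early and/or transferred to other prisons", 2 did not meet the disorder criteria, 3 were buprenorphine-positive and 27 were excluded on medical or psychiatric grounds. That leaves 74 − 9 − 6 − 2 − 3 − 27 = 27 treated. Most or all of the 27 medical or psychiatric exclusions are said to be eligible now, so they belong in the denominator:

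- buprenorphine-positive only: 3/(27 + 27 + 3) = 3/57 = 5%
- early release or transfer only: 6/(27 + 27 + 6) = 6/60 = 10%
- both: 9/(27 + 27 + 9) = 9/63 = 14%

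These are rough. The pilot was not randomised, and the timing of its losses relative to the present randomisation point is unknown.

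**The case against.** The strongest reply is that this is a preference about efficiency, of unknown and possibly trivial size. Losses before release should be similar in both arms, and 6.2 keeps everyone randomised, so the comparison is valid. Section 5.3 already stops people who decline XR-NTX after talking to the physician, which removes much of the refusal before the envelope. The pilot attributes no loss to a failed naloxone or oral naltrexone test. Section 2.7.3 describes the buprenorphine-positive inmates as ineligible for this study, so they may be caught earlier. And 5.4 gives a reason for its order: medication consent follows directly on assignment.

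Most of this stands, and it limits the point to power. It does not remove it. The order in 5.4 still takes medication consent after the arm is announced, so refusal could depend on the arm. Intent-to-treat protects against that, but simply dropping non-starters later would not be safe. The aim in 5.4 can also be met by taking consent just before the envelope is opened.

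A reader might infer that both urine screens come after randomisation. The documents do not establish this. A negative urine is an entry criterion, laboratory tests to confirm eligibility come first, and Figure 3 lists urine toxicology at baseline, so the first screen may come earlier. Nor is actual release an eligibility check: the criterion is being eligible for release within 30 days.

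**Conclusion.** The point holds as a cheap gain in power. On the natural reading, several conditions for starting XR-NTX are settled after randomisation, non-starters stay in both arms, and 6.7 makes no allowance for them. The cost is about one point of power at 2% non-starters and about 13 points at 14%, under the two assumptions stated in the check. The true share is not in the documents.

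Three stronger readings are not supported:

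- **That the stated .80 is wrong.** Section 6.7 gives a detectable population effect and says that it uses no efficacy estimates from earlier studies. If f² = .037 is read as the effect in everyone randomised, power remains .80.
- **That the pilot shows a quarter or more will not start.** Setting the 9 losses against only the 27 treated (9/36 = 25%) leaves out the 27 inmates whom 2.7.3 regards as mostly or all eligible now.
- **That the results would be biased.** Nothing in the documents points to bias in the intent-to-treat comparison.

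Equally, the statement in 1.0 that "all 27 participants got their first injection" gives no reassurance. Those 27 are the people who remained after the pilot's losses, so the figure does not show that everyone randomised here will start.

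**What to change.** In 4.1, 5.3 and 5.4, move the opening of the envelope to the prison injection visit, after medication consent has been given and the injection-day urine and existing challenge tests are negative, ideally straight after the injection. Record earlier losses as screen failures, by reason. Leave 6.2 as everyone randomised. Give the mobile-arm pamphlet at that visit and start confirming the residence from there. State when the first urine screen falls relative to randomisation. None of the checks themselves needs to change.

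**Cost.** Mostly wording. Participants would consent to the prison injection before knowing their arm, which reverses the order in 5.4 and should be clear in the consent discussion. The arm-specific briefing and residence check would fall closer to release. Section 5.6.3 already places the study physician at the prison injection, so the person who opens the envelope should be there. More people must be cleared to randomise 240: 240/(1−q), or 253 at 5% and 280 at 9/63. That is still fewer than the 266 and 327 to be randomised under the present order.

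**What remains.** Losses after the injection but before release are not removed. If the present order is kept, the plan should say how non-starters are handled and reported, and allow for them in the sample size.
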